## Subject Enrollment Count

All subjects enrolled in the clinical investigation (including patients withdrawn from the study before its initiation who have provided informed consent and patients lost to follow-up) must be counted and documented. If a subject withdraws from the study, the reasons should be documented and recorded. These patients will not be included in the sample size calculation for the study or in the primary or secondary objectives.

Patients who are withdrawn from the study before the initiation of the ACTIVA software due to device safety, reliability, or feasibility issues are considered enrolled in the study and will be followed throughout the study's duration.

Patients who discontinue the study during the operation of the ACTIVA software are considered fully enrolled, and all available data will be analyzed.

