### Predicted clinical risks associated with the device and residual risks

The clinical risk associated with the use of the ACTIVA software should not exceed the clinical risk associated with manual control (standard of care). In cases where the results obtained during simulations are not replicated in a clinical setting, it is possible that the software may fail to ensure adequate levels of anesthesia. The principal investigator will decide to interrupt the system and switch to manual mode (current standard of care).

The clinical investigation of the ACTIVA software is the first of its kind for the system, where anticipated adverse events related to the device and risk analysis are the primary focus of this clinical study. During the software development, the primary objective was to eliminate/minimize these risks.

To minimize device-related risks, the ACTIVA software cannot be initiated if the connected devices are not functioning correctly (refer to the user manual). The proper functioning of the control software and its components is indicated on the graphical user interface with a green light, allowing the principal investigator to promptly assess the system's correct operation.

Although the device has undergone extensive testing and simulations during its development, it is possible for it to stop functioning during use. Therefore, the ACTIVA software must be under constant supervision by the investigator, who can detect malfunctions or anomalies through the graphical user interface and take prompt action.

In particular, simulation tests have been conducted to verify that the ACTIVA control system can be interrupted and switched to manual mode (standard of care) in less than 20 seconds. This time period is shorter or overlapping with the time it takes for an anesthesiologist to manage a normal infusion pump that needs to be turned off and restarted and much shorter than the time required to replace a malfunctioning infusion pump.

In the event of a malfunction during drug infusion, the ACTIVA software is capable of promptly alerting the investigator by emitting appropriate auditory and visual signals (red light) on the graphical interface and auditory signals directly from the infusion pumps. Additionally, the investigator can easily and quickly switch to manual control mode for the pumps (see user manual). Examples of malfunctions may include:

- Software freeze/crash.
- Data transmission malfunctions.
- Infusion pump malfunctions.

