### Clinical study description

The clinical study ACTIVA 2 is a pragmatic, interventional, nonrandomized, single-arm, single-center.

The investigation is for research purposes (for publication in scientific journals), non-commercial, and for clinical development of the ACTIVA control software.

The primary outcome measure is the depth of hypnosis adequacy. It is assessed by means of the percentage of the anesthesia maintenance duration in which the BIS is kept inside the recommended range from 40 to 60. The percentage of the anesthesia maintenance duration in which the BIS is kept below 40 is also specified. Maintenance duration is the period of time that goes from the end of anesthesia induction to the point at which the automatic control is turned off at the conclusion of surgery. The end of anesthesia induction is defined as the time instant when the BIS drops below 40 for the first time and remains there for the subsequent 30 seconds.

The secondary outcomes measures are:

- Number and types of dysfunctions of the ACTIVA automatic infusion system.
- Level of satisfaction of the experimenter. It is expressed on a scale from 0 to 10 regarding the ease of use of the ACTIVA software and its infusion system, the induction phase of anesthesia and the maintenance phase of anesthesia.
- Effect of drugs delivery on heart rate. It is assessed by means of the percentage of the anesthesia maintenance duration in which the heart rate (HR) is kept inside the range from 50 to 100 beats per minute. The percentage of the anesthesia maintenance duration in which the HR is kept below 50 is also specified.
- Effect of drugs delivery on mean blood pressure. It is assessed by means of the percentage of the anesthesia maintenance duration in which the non-invasively measured mean blood pressure (MBP) is kept inside the range from 65 to 110 mmHg. The percentage of the anesthesia maintenance duration in which the MBP is kept below 65 is also specified.
- Postoperative heart rate stability. It is assessed by measuring the HR in bpm.
- Postoperative Mean Blood Pressure Stability. It is assessed by non-invasive measuring of the mean blood pressure in mmHg.

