## Number of patients enrolled

The sample size was determined based on the primary outcome measure concerning the depth of hypnosis adequacy provided by the ACTIVA control software. Specifically, it was calculated with the aim to assess the proportion of patients for whom the percentage of the anesthesia maintenance duration in which the BIS is kept inside the recommended range from 40 to 60 is greater than 43%. This latter value is the average percentage that was observed in a previous data acquisition campaign concerning manually controlled TIVA, which was performed in the same clinical setting considered for the present clinical trial (Study acronym: ACTIVA 1, Id code: NP-1843).

The proportion was estimated to be 90% of patients with a 95% confidence interval and a margin of error of 10%. The resulting sample size is 139 patients. This number of enrolled subjects also ensures that the ACTIVA control software is adequately tested for safety, reliability, feasibility, and applicability. Secondary outcome measures were not considered in the sample size calculation.

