## Systematic errors prevention methods

### Interaction between the ACTIVA software and the experimenter.

The user interface has been developed to make it easy for the experimenter to initiate the infusion system. Specifically, once the necessary connections between the monitor, PC, and infusion pumps have been set up, the experimenter can start the ACTIVA software and quickly check for any issues with the system. The software only starts when the experimenter has entered all the required data for startup, and the connections between the devices are correct and functioning. If the experimenter has not entered all the required data or if the devices are not functioning correctly or have not been turned on, the ACTIVA software cannot begin the infusion phase. This ensures both adequate safety and prevents incorrect or incomplete operation.

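### Patients in whom ACTIVA cannot be started because of a software problem can drop out of the reliability and applicability result

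*Protocol*

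**What the plan says.** The protocol section Subject Enrollment Count has three paragraphs.

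- The first requires that all enrolled subjects be counted and documented. It names consented patients withdrawn before initiation and patients lost to follow-up, asks for the reasons for any withdrawal, and ends: "These patients will not be included in the sample size calculation for the study or in the primary or secondary objectives". It makes no exception for device causes.
- The second covers a narrower group: "Patients who are withdrawn from the study before the initiation of the ACTIVA software due to device safety, reliability, or feasibility issues are considered enrolled". They are to be followed, but nothing is said about analysis.
- The third covers patients who stop while ACTIVA is running. They count as fully enrolled and their available data are analysed.

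A second rule stands under Deviations from the clinical evaluation plan. A regularly enrolled patient who does not complete because of ACTIVA software issues, or at the investigator's discretion, is left out of the secondary outcome measures and kept for the primary.

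Reliability, safety and applicability form the secondary objective. The first secondary outcome is "Number and types of dysfunctions of the ACTIVA automatic infusion system", with no denominator. A blocked start is foreseen: "the ACTIVA software cannot be initiated if the connected devices are not functioning correctly", and with missing data or faulty or switched-off devices "the ACTIVA software cannot begin the infusion phase".

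The SAP section Population to be analyzed repeats eligibility and procedure text and defines no analysis set.

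**The concern.** A device that cannot be started is direct evidence about reliability and applicability. If such patients are left out, the dysfunction result describes only sessions that passed the system's own start check, and the omission can only favour the device. The protocol also says of its 139 patients: "This number of enrolled subjects also ensures that the ACTIVA control software is adequately tested for safety, reliability, feasibility, and applicability". That claim is weaker if the count leaves out patients in whom the software did not get as far as running.

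Because the status of these patients is not settled, the choice could also be made after the events are known.

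**Working it through.** **The plan's own figure.** Inputs from Number of patients enrolled: "The proportion was estimated to be 90% of patients with a 95% confidence interval and a margin of error of 10" per cent, and "The resulting sample size is 139 patients". The Wald formula is n = z² p(1 − p)/d², with z = 1.95996 and p = 0.90.

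- d = 0.05: 3.84146 × 0.09 / 0.0025 = 138.29, rounded up to 139. This matches.
- d = 0.10: 3.84146 × 0.09 / 0.01 = 34.57, rounded up to 35. This does not match.

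So 139 reproduces when the 10% is the full width of the interval. That is a separate matter of wording. What counts here is that the calculation makes no allowance for start failures and does not address the dysfunction outcome.

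**A patient withdrawn before start-up because of the software, under each rule.**

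| Rule | Primary outcome | Dysfunction outcome |
|---|---|---|
| Enrollment Count, first paragraph read literally | Out | Out |
| Enrollment Count, second paragraph read as an exception | Not stated | Not stated; in, if enrolled implies analysed |
| Deviations section, non-completion because of ACTIVA software | In by rule, but no value exists | Out |

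The primary outcome is a percentage of the maintenance period, which ends when automatic control is turned off. A patient never placed under automatic control has no such period. The deviations rule therefore keeps this patient only for an outcome that cannot be computed, and drops the patient from the one the failure bears on. The exception reading of the second paragraph does not undo this, because the deviations rule applies to enrolled patients.

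The deviations rule also conflicts with the third enrollment paragraph. A session stopped by a software fault is analysed with all available data under one and left out of the secondary outcomes under the other.

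**Illustration of size.** The documents give no start-failure rate. Assume 139 started sessions and s device-caused start failures in addition. Without these patients, start failures are zero by construction. With them the rate is s/(139 + s):

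- s = 3: 3/142 = 2.1% (exact 95% interval 0.4% to 6.0%)
- s = 7: 7/146 = 4.8% (1.9% to 9.6%)
- s = 14: 14/153 = 9.2% (5.1% to 14.9%)

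The intervals are Clopper-Pearson and are added here for scale. The plan is descriptive and reports none.

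**The case against.** The best defence is that the second enrollment paragraph is an exception to the first. The first already counts consented, withdrawn patients among the enrolled, so calling the device-related group enrolled adds little unless it changes their status. The first paragraph can also be read as being about withdrawal before the study begins for the patient, whereas the second is about the start of the software. The protocol (Measured variables) and the SAP (Analyses) collect system dysfunctions for each enrolled patient, and the SAP describes all study variables. On that reading start failures would be in.

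This is plausible, and Subject Enrollment Count alone does not decide the matter. The defence fails at the deviations section, which removes software-related non-completers from the secondary outcomes on either reading.

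Three further points stand.

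- A reader might infer that the first two enrollment paragraphs contradict each other. They do not: a patient can be enrolled and followed yet not analysed.
- A reader might infer that any set-up fault always ends as a withdrawal before start. The start check also responds to missing entries or devices not switched on, which can be corrected. Monitor and pump faults are not attributed to ACTIVA; the protocol says they are recorded, evaluated with the results, and resolved by repair or replacement.
- Reliability problems have other routes: monthly monitoring, manufacturer inspection, and suspension or termination. These protect conduct but do not put the event into the reported result.

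**Conclusion.** The concern holds in this form: followed as written, software-caused failures to start can be lost from the reliability and applicability result, and the loss favours the device. The main support is the deviations rule, together with the missing primary value; the literal wording of the first enrollment paragraph adds to it. For start failures caused by the monitor or pumps, the exclusion is less certain and depends on how the enrollment paragraphs, or the investigator-discretion clause, are read.

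The size is unknown. The range of 2.1% to 9.2% rests wholly on assumed counts of 3 to 14. A reader might go further and conclude that the reliability result is biased by a known amount, or that the proportion of patients above 43% of maintenance time in range is overstated. The documents support neither. They give no failure count, and that proportion is the basis of the sample size, not a listed outcome.

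The BIS, heart rate and blood pressure percentages are unaffected, since they exist only for started sessions. The point is worth correcting because reliability is a stated objective and the remedy is cheap.

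**What to change.** 1. Protocol, Subject Enrollment Count: limit the exclusion to patients withdrawn before start-up for reasons unrelated to the device, and give the analysis status of the device-related group.
2. Protocol, Deviations from the clinical evaluation plan: keep device-related non-completers in the dysfunction outcome, and reconcile this rule with the third enrollment paragraph. Changing Subject Enrollment Count alone would leave the deviations rule in force.
3. SAP, Population to be analyzed: state that every consented patient in whom ACTIVA start-up was attempted is in the dysfunction denominator.
4. List device-caused failure to start as a dysfunction type, reported as n/N attempted. Record it separately from monitor or pump faults that the protocol does not attribute to ACTIVA.
5. Keep the BIS, heart rate and blood pressure percentages on started sessions.

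Optional additions are an exact interval for the start-failure rate and a sensitivity line that counts device-caused start failures as not exceeding 43%.

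The cost is wording in three places and one table row. Withdrawals and their reasons must already be documented and the device-related group followed, so little new data is needed. The downside is a slightly less favourable reliability figure if start failures occur.

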## Deviations from the clinical evaluation plan

Except in cases of necessity, the principal investigator is not authorized to deviate from the clinical protocol. Deviations from the clinical evaluation plan that are decided upon by the investigator to protect the rights, safety, and health of the patient will be documented and communicated to the manufacturer and the sponsor as soon as possible.

The sponsor will define the level of deviations as major or minor and will present them to the relevant Ethics Committee for evaluation accordingly. Major deviations are defined as changes in the conduct of the clinical investigation compared to the current protocol that could compromise the subject's rights, safety, health, completeness, accuracy, or scientific integrity of the data.

Deviations should be reported to the principal investigator and recorded in the patient's chart. Cases where a regularly enrolled patient does not complete the study due to ACTIVA software issues or at the investigator's discretion are not considered deviations; the patient will not be considered for secondary outcome measures but will be evaluated for the primary outcome measure.

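### The protocol's rules on withdrawn and non-completing patients can remove device failures, before or after start, from the secondary outcome that is meant to count them

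*Protocol*

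**What the plan says.** Subject Enrollment Count in the protocol has three paragraphs.

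- The first requires every enrolled subject to be counted, "including patients withdrawn from the study before its initiation who have provided informed consent and patients lost to follow-up". It asks for the reasons when a subject withdraws, and then states: "These patients will not be included in the sample size calculation for the study or in the primary or secondary objectives". It makes no exception for withdrawals caused by the device.
- The second takes up "Patients who are withdrawn from the study before the initiation of the ACTIVA software due to device safety, reliability, or feasibility issues" and says that they "are considered enrolled in the study and will be followed throughout the study's duration". It is silent on analysis.
- The third concerns patients who stop while the software is running. They "are considered fully enrolled, and all available data will be analyzed".

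Two other protocol sections bear on the same patients. Deviations from the clinical evaluation plan deals with regularly enrolled patients who do not complete, either because of problems with the software or by the investigator's choice: "the patient will not be considered for secondary outcome measures but will be evaluated for the primary outcome measure". Selection bias at the time of analysis leaves it to the experimenter to judge whether data collected up to an interruption can be used.

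The outcome concerned is the first secondary outcome under Clinical study description: "Number and types of dysfunctions of the ACTIVA automatic infusion system". Reliability is part of the secondary objective. A blocked start is foreseen: "the ACTIVA software cannot be initiated if the connected devices are not functioning correctly".

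The SAP section Population to be analyzed repeats the eligibility criteria and the procedure. It defines no analysis set, and the Analyses section specifies descriptive statistics only.

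**The concern.** A reliability outcome needs a denominator that includes the patients in whom the system failed. Here the patients most likely to supply a dysfunction are those whose anesthesia could not be started under ACTIVA, or could not be finished under it, because of the system. The rules point in different directions for them, and at least one rule removes them from the secondary outcomes.

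If dysfunctions are counted only in patients whose system started and ran to the end, the result is conditioned on success, and the error can only favour the device. Because the text allows more than one reading, the choice could also be made after the failures are known. This matters because the protocol states, under Number of patients enrolled, that its sample size is enough to test safety, reliability, feasibility and applicability.

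**Working it through.** **1. The rules side by side**

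| Patient | Subject Enrollment Count | Deviations section | In the dysfunction count? |
|---|---|---|---|
| Withdrawn before start, non-device reason | Paragraph 1: outside both objectives | Not addressed | No; uncontroversial |
| Withdrawn before start, device reason | Paragraph 1, read broadly: outside both objectives. Paragraph 2: enrolled and followed, analysis not mentioned | If enrolled and not completing because of the software: outside secondary outcomes, inside primary | Excluded or undefined |
| Stopped during operation because of the software | Paragraph 3: all available data analysed | Outside secondary outcomes, inside primary | Contradictory |
| Started, lost to the 6 h or 24 h visit | Paragraph 1, read broadly: outside both objectives | Not addressed | Unclear |

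The second row leads to the same place on either reading of paragraph 1. Read broadly, that paragraph excludes these patients. If paragraph 2 is an exception to it, they are enrolled, and the deviations section then removes from the secondary outcomes those who do not complete because of the software. No sentence places them in the dysfunction count.

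The deviations rule also cannot be applied as written to a patient whose software never started. It asks for evaluation on the primary outcome, but that outcome is a percentage of the maintenance period, which ends when automatic control is turned off. Without a start there is no such period under closed-loop control.

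**2. The plan's own figure**

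The sample size inputs are an expected proportion p = 0.90, a 95% confidence level (z = 1.96) and a margin of 10%, with a stated result of 139. The precision formula is n = z² p(1 − p) / d².

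- d = 0.05 (10% as the full width of the interval): 3.8415 × 0.09 / 0.0025 = 138.3, rounded up to 139. This reproduces the plan.
- d = 0.10 (10% as the half-width): 3.8415 × 0.09 / 0.01 = 34.6, rounded up to 35. This does not.

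The present point does not depend on this calculation. The 139 is used below only as a denominator.

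**3. Illustration of size**

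The number of start failures, k, is not in the documents and is an assumption. They are taken to be among the 139 enrolled. Intervals are exact (Clopper-Pearson) 95%.

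| k | Counted: k/139 | Excluded, no other dysfunction |
|---|---|---|
| 1 | 0.7% (0.0 to 3.9%) | 0/138 = 0% (upper limit 2.6%) |
| 3 | 2.2% (0.4 to 6.2%) | 0/136 = 0% (upper limit 2.7%) |
| 5 | 3.6% (1.2 to 8.2%) | 0/134 = 0% (upper limit 2.7%) |
| 14 | 10.1% (5.6 to 16.3%) | 0/125 = 0% (upper limit 2.9%) |

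The 0% requires that no other patient has a dysfunction. If 5 other patients have one, k = 3 gives 8/139 = 5.8% counted against 5/136 = 3.7% excluded, and k = 5 gives 10/139 = 7.2% against 5/134 = 3.7%. The figure is then above zero but still too low.

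The plan defines the outcome as a number and a list of types, not as a rate per patient. The percentages are a convenient scale for the loss; the count itself would fall by k.

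**The case against.** **The exclusion sentence may be narrower than it looks.** It directly follows the sentence about a subject who withdraws, so it may be a general rule for withdrawals, with paragraphs 2 and 3 as special cases. A reader might infer a flat contradiction between paragraphs 1 and 2; the wording does not establish one. This stands. It does not rescue the outcome, because paragraph 2 grants only enrolment and follow-up, and the deviations section still applies.

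**Loss to follow-up.** A reader might also infer that the plan discards complete BIS data when a patient misses the 24-hour visit. That depends on the same unclear reference. Patients lost to follow-up appear only in the parenthesis on who must be counted, so the exclusion may not reach them. This supports a request for clarification, not a finding that valid primary data are thrown away.

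**Not every blocked start is a device failure.** The block is presented as a safeguard. According to Interaction between the ACTIVA software and the experimenter, it also acts when required data have not been entered or a device is not switched on. Factors that may compromise the outcome and interpretation of the results says that monitor and pump malfunctions are not attributed to the software, though they are to be recorded and evaluated. Both points stand and shape the fix. Paragraph 2 may also cover consented patients who were waiting when the study was suspended, so its group is not identical to failed starts.

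**The stakes are limited.** This is a descriptive secondary outcome with no decision rule, it played no part in the sample size, and the number affected may be zero. That limits the size of the problem. It does not supply a denominator.

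**Conclusion.** The concern holds in this form: the rules under Subject Enrollment Count, Selection bias at the time of analysis and Deviations from the clinical evaluation plan do not agree, and they can remove device failures, before or after start, from the dysfunction outcome. The firmest part is the conflict between the deviations section and the third paragraph of Subject Enrollment Count, which does not depend on any unclear pronoun. The SAP does not resolve it.

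The direction of the effect is known: if such failures occur and are excluded, reported reliability is too favourable. The size is not known. With an assumed 3 to 5 start failures among 139 and no other dysfunction, 2.2 to 3.6% would be reported as 0%. The documents do not show that any bias has occurred.

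The change should be made because it is cheap and concerns a stated objective. It affects neither the sample size nor the design.

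**What to change.** Reconcile the three protocol sections and state the following in the SAP section Population to be analyzed:

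- **Dysfunction outcome.** Report it in all patients in whom an ACTIVA start was attempted, including those who never started or did not complete because of the system. Count a failure to start when a system fault caused it, and report it by type (software, communication, pump, monitor). Show pump and monitor faults separately, in line with the protocol's statement on attribution. Do not count a block caused only by incomplete data entry or a device not switched on.
- **Primary outcome.** Analyse it in all patients in whom automatic control started and a maintenance period exists, whether or not the 6 h and 24 h visits took place. Reword the first paragraph of Subject Enrollment Count so that loss to follow-up does not remove complete BIS data.
- **Left out of the analyses.** Only patients withdrawn before any start attempt for reasons unrelated to the device.

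In the deviations section, remove or limit the exclusion from secondary outcomes so that it no longer applies to the dysfunction count. Replace the experimenter's case-by-case judgement on interrupted procedures with the rules above.

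The cost is a rewording of three protocol sections and one SAP section. The downside is that the reported dysfunction figure may be slightly less favourable.
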